**Number of planned patients**

In total 9 patients will be enrolled to receive a first treatment cycle in an ascending dose study of CLS12311. 6 of these patients will receive a second treatment cycle once safety of the first treatment cycle has been confirmed.

Timelines	
The total duration of study participation in Part A for each subject will be at least 48 weeks. Subject eligibility will be determined at Baseline (visit 1, week 0), followed by a 17-week treatment phase and a 31-week safety follow up phase.
 
The duration of the study is expected to be approx. 20 months. The end of this study is defined as the date when the last patient, last visit (LPLV) occurs.

Patient population	
The study population will consist of patients with a diagnosis of RRMS in accordance with the revised 2017 McDonald Criteria. Patients previously treated with MS drugs will be allowed to participate in this study provided that they did not take certain medications within the timeframes defined in the exclusion criteria.
 
Given MS's gender and age distribution, with females affected up to three times more than males, the study population is expected to have a higher proportion of females.

Study location	The study will be performed at approximately 12 sites in Europe.
Main inclusion criteria	
General inclusion criteria (to be assessed at the beginning of the baseline period based on patient interview and medical history):
 
 
1. RRMS according to the 2017 McDonald criteria
 
2. Male or female patients (assigned at birth) aged 18-55 years inclusive
 
3. Disease duration (since diagnosis) <10 years
 
4. EDSS at baseline 0-5.5
 
5. Untreated patients or patients being off therapy for the time periods listed under exclusion criterion No. 2. Patients are either not eligible to receive approved therapies or have explicitly chosen not to receive such therapies after being adequately informed by the investigators
 
6. Only for sexually active female patients of childbearing potential (sexually mature, pre-menopausal and not surgically sterile): the patient is willing to use a highly effective method of contraception (defined in the study protocol) throughout the complete treatment phase or at least for 4 weeks after the last dose of CLS12311
 
7. Male patients willing to use contraception (condoms) throughout the complete treatment phase or at least for 4 weeks after the last dose of CLS12311, unless surgically sterile
 
8. Basic immunization against SARS-CoV-2, i.e. both doses of two-dose vaccines (or one dose of a vaccine and a SARS-CoV-2 infection before or after vaccination) OR a dose of a single-dose vaccine
 

Main exclusion criteria	
General exclusion criteria (to be assessed at the beginning of the baseline period based on patient interview and medical history):
 
 
1. Patients with an active chronic disease (or stable but treated with immunomodulatory/-suppressive therapy) of the immune system other than MS (e.g. rheumatoid arthritis, scleroderma, Crohn's disease, ulcerative colitis, etc.) or with a known immunodeficiency syndrome (AIDS, hereditary immune deficiency, drug-induced immune deficiency)
 
2. Prior treatment with any of the medications below within the specified time-frame: 
 
a. glatiramer acetate, interferon-beta within 4 weeks prior to screening visit 1
 
b. dimethylfumarate, diroximel-fumarate within 4 weeks prior to screening visit 1
 
 
 

	
 
c. teriflunomide within 4 weeks prior to screening visit 1, provided accelerated elimination procedure (eg. cholestyramine) was performed and teriflunomide plasma level are below 0.02 mg/L before randomization
 
d. fingolimod, ozanimod within 12 weeks prior to screening visit 1, provided normal lymphocyte counts (see exclusion criterion No. 18)
 
e. siponimod, ponesimod within 8 weeks prior to screening visit 1, provided normal lymphocyte counts (see exclusion criterion No. 18)
 
f. natalizumab within 12 weeks prior to screening visit 1
 
g. ocrelizumab, ofatumumab, rituximab, alemtuzumab, cladribine, mitoxantrone within 52 weeks prior to screening visit 1
 
h. plasma exchange, intravenous immunoglobulin within 8 weeks prior to screening visit 1
 
i. azathioprine, methotrexate, cyclophosphamide or any other continuous immunosuppressive therapy within 24 weeks prior to screening visit 1
 
j. any other immunosuppressive monoclonal antibody treatment within 24 weeks prior to screening visit 1
 
k. Prior autologous hematopoietic stem cell transplantation
 
l. Corticosteroid treatment for MS relapse within 4 weeks prior to screening visit 1
 
m. Patients who participated in the ETIMSred trial
 
 
 
3. History of HIV, chronic or active Hepatitis C, chronic or active Hepatitis B or prior Syphilis, which has not been sufficiently treated
 
4. Long-Covid19 syndrome
 
5. History of splenectomy or chronic liver disease
 
6. History of coronary artery disease, chronic heart failure, aortic stenosis
 
7. Current anticoagulation therapy
 
8. Uncontrolled grade II hypertension (<math>\geq 160</math> systolic and/or <math>\geq 100</math> diastolic blood pressure; according to ISH global practice guidelines) despite treatment or without treatment
 
9. History of stroke
 
10. Pregnant female confirmed by a positive pregnancy test or breast-feeding
 
11. History of alcohol or drug abuse within the 1 year prior to screening visit 1
 
12. History of or existing malignancy within the last 5 years prior to enrollment except history of basal cell carcinoma and melanoma in situ
 
13. History of or existing relevant central nervous system disorder (other than MS)
 
14. Allergy to gadolinium-based contrast agents
 
15. Any other disease or condition, which could interfere with the participation in the study according to the study protocol, or with the ability of the patients to cooperate and comply with the study procedures
 
 
Specific exclusion criteria (to be assessed during the baseline period):
 
 
16. Anemia, defined as hemoglobin levels <math>\leq 12.5</math> g/dl (7.25 mmol/l) for female and <math>\leq 13.5</math> g/dl (8.37 mmol/l) for male participants (may be repeated if 11.5 -12.5 g/dl in females and 12.5 - 13.5 g/dl in males)
 

--	---

	
17. Erythrocyte count <4.0 E12/L in female and <4.5 E12/L in male patients (may be repeated if >3.8 E12/L in female and >4.3 E12/L in male)
 
18. Lymphopenia with total lymphocyte counts ≤1000/μl (may be repeated if >800/μl)
 
19. Positive HIV testing
 
20. Positive results of baseline period testing for serological markers for hepatitis B, C, and Syphilis indicating acute or chronic infection
 
21. Patient is not eligible for blood donation according to local regulations
 
22. Having one or more of the following laboratory results:
 
 
Estimated glomerular filtration rate (eGFR) < 60 mL/min/1.73 m^2 (may be repeated if eGFR is 45–59 mL/min/1.73 m^2)
 
ALT or AST > 3 × upper limit of normal (ULN; may be repeated if 3.1–4 × ULN)
 
Total bilirubin greater than 2 × ULN (may be repeated if 2.1–3 × ULN), with the exception for patients with Gilbert's disease
 
Platelet count ≤ 100 × 10^9/L (may be repeated if 80–100 × 10^9/L)
 
Abnormalities in hepatic synthetic function tests (PT time, INR, PTT, albumin) as judged by the Investigator to be clinically significant
 

Investigational product(s), formulation, route of administration	
The drug product CLS12311 consists of autologous red blood cells (RBCs) that have been chemically coupled with [REDACTED] peptides [REDACTED] [REDACTED] from [REDACTED] proteins [REDACTED] expressed in the brain and re-suspended in saline (150 ml).
 
Placebo consists of autologous red blood cells (RBCs) re-suspended in saline (150 ml).
 
CLS12311 and placebo are stored in standard bags for blood transfusions.
 
CLS12311 and placebo will be administered by i.v. infusion typically over a 30 to 60 minutes period.

Dosing	
Single/first treatment cycle of CLS12311 will be given as follows:
 
 
Group 1 (2 patients): 
 
[REDACTED] 
 
Bag 1: [REDACTED] peptide-coupled RBCs (CLS12311)
 
Bag 2: [REDACTED] uncoupled RBCs (placebo)
 
 
 
Week 3: 
 
Bag 1: [REDACTED] uncoupled RBCs (placebo)
 
Bag 2: [REDACTED] uncoupled RBCs (placebo)
 
 
 
 
manufactured from a single blood donation [REDACTED]
 
 
Group 2 (3 patients): 
 
[REDACTED] 
 
Bag 1: [REDACTED] peptide-coupled RBCs (CLS12311)
 
Bag 2: [REDACTED] uncoupled RBCs (placebo)
 
 
 
[REDACTED] 
 
Bag 1: [REDACTED] peptide-coupled RBCs (CLS12311)
 
Bag 2: [REDACTED] uncoupled RBCs (placebo)
 
 
 
 
manufactured from a single blood donation [REDACTED]
 
 
Group 3 (4 patients): 
 
[REDACTED]
 
 
 

	
 
▪ Bag 1: [REDACTED] peptide-coupled RBCs (CLS12311)
 
▪ Bag 2: [REDACTED] peptide-coupled RBCs (CLS12311)
 
○ [REDACTED] 
 
▪ Bag 1: [REDACTED] peptide-coupled RBCs (CLS12311)
 
▪ Bag 2: [REDACTED] peptide-coupled RBCs (CLS12311)
 
 
 
 
manufactured from a single blood donation [REDACTED]
 
Second treatment cycle of CLS12311 will be given as follows:
 
 
• Group 1 (1 patient): 
 
○ [REDACTED] 
 
▪ Bag 1: [REDACTED] peptide-coupled RBCs (CLS12311)
 
▪ Bag 2: [REDACTED] uncoupled RBCs (placebo)
 
 
 
○ [REDACTED] 
 
▪ Bag 1: [REDACTED] uncoupled RBCs (placebo)
 
▪ Bag 2: [REDACTED] uncoupled RBCs (placebo)
 
 
 
 
manufactured from a single blood donation [REDACTED]
 
• Group 2 (2 patients): 
 
○ [REDACTED] 
 
▪ Bag 1: [REDACTED] peptide-coupled RBCs (CLS12311)
 
▪ Bag 2: [REDACTED] uncoupled RBCs (placebo)
 
 
 
○ [REDACTED] 
 
▪ Bag 1: [REDACTED] peptide-coupled RBCs (CLS12311)
 
▪ Bag 2: [REDACTED] uncoupled RBCs (placebo)
 
 
 
 
manufactured from a single blood donation [REDACTED]
 
• Group 3 (3 patients): 
 
○ [REDACTED] 
 
▪ Bag 1: [REDACTED] peptide-coupled RBCs (CLS12311)
 
▪ Bag 2: [REDACTED] peptide-coupled RBCs (CLS12311)
 
 
 
○ [REDACTED] 
 
▪ Bag 1: [REDACTED] peptide-coupled RBCs (CLS12311)
 
▪ Bag 2: [REDACTED] peptide-coupled RBCs (CLS12311)
 
 
 
 
manufactured from a single blood donation [REDACTED]
 

Statistical methods	
Sample Size Calculation	
As this is an exploratory Phase Ib study focusing on safety and tolerability, no formal sample size calculation has been performed.
 
The number of patients enrolled is considered sufficient to evaluate the safety and tolerability of CLS12311 and to collect preliminary exploratory biomarker data. The study is not powered for efficacy analyses.

Analysis Populations	
 
• The enrolled analysis set includes all patients who provided informed consent.
 
• The safety analysis set (SAF) includes all patients with blood donation for CLS12311 production.
 

Safety analysis	
Adverse events (AE) will be coded using MedDRA and will be presented by primary System Organ Class (SOC) and Preferred Term. The analysis will focus on the treatment-emergent AEs (TEAE), i.e. AEs which started or worsened after blood donation for CLS12311 production. The frequency of TEAEs by dose group and in total will be summarized by incidences standardized to the number of patients at risk and rates standardized to the total observation time.

	
Frequencies of TEAEs by dose group and in total will also be presented by relationship to study treatment and by severity. Additional analyses will be performed for SAE, TESAE, adverse events of special interest (AESIs) and AEs leading to discontinuation.
 
The number and percentages of patients having experienced a centrally confirmed relapse will be presented by dose group and in total.
 
Descriptive summaries of observed values and changes from baseline will be presented for hematology and biochemistry variables by dose group. Each abnormal value will be flagged to show whether it is a value below or above the reference range and assessed by the Investigator for clinical relevance. The assessments of laboratory variables will be tabulated by visit for each clinical laboratory analyte by dose group and in total (frequency tables).
 
The assessment of categorical urinalysis variables will be tabulated by visit for each urine parameter by dose group and in total (frequency tables).
 
Vital signs will be described by summary statistics (by dose group and in total) for measured values and changes from baseline by visit.
 
The number and percentages of patients with normal/abnormal findings in physical examinations will be presented by visit (by dose group and in total).
 
Additional safety analyses will examine the changes in clinical parameters including EDSS, 9-HPT, T25-FW and SDMT following treatment with CLS12311.

Further analyses	
Exploratory analyses will include quantitative and functional aspects of the obtained T cell responses as well as analysis of the influence of dose on other immune cell populations such as regulatory T cells and changes in soluble biomarkers. Biomarker data may also be explored in relation to safety and imaging parameters. All analyses will be exploratory and hypothesis-generating.

Safety analysis timepoints	
The safety evaluation will be conducted by the Sponsor's Medical Expert(s) and/or the Data Safety Monitoring Board.
 
Safety will be assessed at different timepoints:
 
Single/First treatment cycle
 
 
• After each patient in the low dose group completed [REDACTED]
 
• After each patient in the medium dose group completed [REDACTED]
 
• After each patient in the high dose group completed [REDACTED]
 
• After sentinel patients 3 and 6 completed [REDACTED]
 
• Data Safety Monitoring Board (DSMB) meeting after the last patient in the high dose group completed [REDACTED]
 
 
Second treatment cycle
 
 
• After all patients in the low dose group completed [REDACTED]
 
• After the first patient (sentinel) in the medium dose group completed [REDACTED]
 
• After all patients in the medium dose group completed [REDACTED]
 
• After the first patient (sentinel) in the high dose group completed [REDACTED]
 
• After the last patient in the high dose group completed [REDACTED]
 

Data and Safety Monitoring (DSMB)	
A DSMB consisting of at least 3 independent MS- and trial-experienced neurologists will be established to closely monitor the safety of the trial. Besides tolerability and safety of CLS12311, the DSMB will also evaluate

worsening of MS assessed by new lesions on brain MRI and occurrence of relapses and progression of disability based on EDSS.

After the last patient in the high dose group completed [REDACTED] and [REDACTED], the DSMB will evaluate all safety data (including MRI and clinical data).

In addition, a DSMB meeting will be required any time during the trial, if any of the criteria mentioned below is met:

- if at least 1 patient experiences AE graded as severe and at least possibly related to the IMP within the same dose level of CLS12311 or placebo
- if at least 3 patients experience AEs graded as 'moderate' and at least possibly related to the IMP within the same dose level of CLS12311/placebo
- If at least 3 patients (irrespective of the dose group) show an increase of >5 new lesions (CEL or new/enlarging T2) at [REDACTED] compared to the average number of new brain lesions (as defined above) observed during baseline
- if a confirmed relapse (irrespective of the dose group), assessed as severe, occurred within 4 weeks after the last dosing

The DSMB shall give recommendations on the following main outcomes:

- stop further treatment or lower further dosing in individual patients
- stop recruitment and/or treatment or lower dose for a specific treatment arm
- stop recruitment and/or treatment for the clinical trial
- continue the clinical trial as per protocol
- any other trial modification (e.g. additional visits, assessments)

Any recommendation will be explicitly documented in the meeting minutes.

Based on the DSMB recommendations, the Study Steering Committee will decide on actions to be taken as outlined above.

For the DSMB meetings, the DSMB will receive patient listings and statistical summaries, consisting of at least the following in addition to all available data on the patient(s) that made the meeting necessary:

- All patients who experienced SAEs (including relationship and severity)
- All patients who experienced AEs (including relationship and severity)
- All patients who experienced AEs within one day following infusion of CLS12311/placebo including severity and relationship
- All patients who experienced a relapse
- Number of new brain lesions (CEL and new/enlarging T2)
- EDSS scores
- Safety relevant protocol deviations

Detailed requirements on the presentation of listings and summaries and details of the premise and the scope of the DSMB will be specified in the DSMB Charter.

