### 13.1.2 Serious Adverse Event (SAE)

Any untoward medical occurrence or effect that, at any dose

- Results in death
- Is life-threatening
- Requires inpatient hospitalization or prolongation of existing hospitalization
- Results in persistent or significant disability or incapacity
- Is a congenital anomaly/birth defect
- Is a medically important event

More than one of the above criteria can be applicable to the same event.

AEs/ARs that are not immediately life-threatening or do not result in death or hospitalization but may jeopardise the patient or may require intervention to prevent serious outcome as defined above, are also classified as serious. Example: Any suspected transmission of an infectious agent via a medicinal product should be considered as a serious adverse reaction.

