### 13.1.3 Adverse Event Intensity

The intensity or severity of an adverse event will be classified based on the Common Terminology Criteria for Adverse Events (CTCAE, version 5.0, 2017) (Table 13-1). Care needs to be taken to avoid confusing the term "severe" with the classification of "serious" (see section 13.1.2). Appropriate training should be provided to the investigational site staff as required.

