**Table 13-1 Adverse event intensity classification**

Severity	Explanation
Mild (Grade 1)	

• Asymptomatic or mild symptoms

• Clinical or diagnostic observations only

• Intervention not indicated

Moderate (Grade 2)	

• Minimal, local or non-invasive intervention indicated

• Limiting age-appropriate instrumental activities of daily living (ADL)

Severity	Explanation
Severe (Grade 3)	
 
Severe or medically significant but not immediately life-threatening
 
Hospitalization or prolongation of hospitalization indicated
 
Disabling
 
Limiting self-care activities of daily living
 

Life-threatening (Grade 4)	
 
Life-threatening consequences
 
Urgent intervention indicated
 

Death (Grade 5)	
 
Death related to AE
 

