#### 13.4.6 Risks of Manufacturing and Transportation

The IMP/placebo will be manufactured, tested, and released in compliance with GMP requirements including appropriate sterility testing. Nonetheless, there is still a risk that manufacturing of the IMP/placebo will have to be stopped or that the final product will not be conforming to specifications and can be not released for use. Despite all due care, there is a certain risk of the possible transmission of germ components. Furthermore, there is also the risk of damage to the starting product or the final product due to incorrect handling or exceeding of the expiry date e.g. due to prolonged transport times so that the starting product can no longer be used for manufacturing, or the final product can no longer be used for infusion. In these cases, study treatment cannot be carried out as scheduled. The management of positive sterility test results during manufacturing and after administration of IMP to a patient is illustrated in Appendix 24.7.

There is also a minor risk of mixing up patient blood and IMP/placebo. Safety measures have been taken to minimise the risk and to ensure that the patient will receive the own IMP/placebo. This also includes serological crossmatch or bedside testing immediately prior to each infusion according to the local regulations. In case of incompatibility the IMP/placebo will not be infused.

If study treatment cannot be carried out as scheduled, the patient will stay on study and receive his/her next treatment according to the study schedule.

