#### 19.1.4 Steering Committee

A Steering Committee consisting of at least the Sponsor and selected country Investigators, or other experts will be established to provide oversight of the conduct of the trial. This includes oversight of the practical aspects of the study as well as ensuring that the study is conducted in a way which is both safe for the patients and provides appropriate safety and efficacy data to the Sponsor and Investigators.

Specific responsibilities of the Steering Committee may include, but are not limited to, the following:

- to provide overall supervision of the trial, including compliance with regulatory standards
- to discuss steps to reduce deviations from the protocol
- periodic review of the study progress
- to review safety data; in a blinded manner. This review is typically done blinded to treatment allocation

- to resolve any differences within the research team or between research team and Sponsor regarding data management and monitoring procedures in the trial or any recommendation for modifications to the protocol.
- The Steering Committee provides guidance to the Sponsor regarding modifications of the trial conduct based on DSMB recommendations, e.g. prematurely stopping recruitment and/or treatment, reducing the dose for a specific dose group or terminating the clinical trial.

Details regarding composition of the Steering Committee, its premise and scope will be specified in the Steering Committee charter. Members will agree their commitment to the charter in writing prior to the start of the study.

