## 24.7 Handling of sterility testing positive results in/during manufacturing and after IMP administration

### Part 1: Overview about microbiological testing

[figure not shown]

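### No DSMB trigger uses seriousness, so a single related serious adverse event graded below 3 does not by itself require the board to meet before its first scheduled review (a narrow gap, cheap to close)

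*Protocol*

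**What the plan says.** The DSMB row of the synopsis (Protocol Section 3) says when a meeting is required outside the schedule. There are four criteria:

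1. One patient with a severe related event at a dose level: "if at least 1 patient experiences AE graded as severe and at least possibly related to the IMP".
2. Three patients with moderate related events at the same dose level.
3. Three patients with an increase of more than 5 new brain lesions over baseline.
4. A confirmed severe relapse within 4 weeks after the last dosing.

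Serious events appear in that row only among the listings the board receives once it meets. Section 13.1.3 grades severity by CTCAE and tells sites to keep severe apart from serious. Table 13-1 describes Grade 3 as "Severe or medically significant but not immediately life-threatening". Section 13.1.2 defines seriousness separately. It includes medically important events and gives this example: "Any suspected transmission of an infectious agent via a medicinal product should be considered as a serious adverse reaction".

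The first scheduled DSMB meeting comes after the last high-dose patient reaches a redacted milestone (synopsis; Sections 7.1 and 19.1.3). Before that, the sponsor's medical experts decide on each escalation (Section 19.1.3). The synopsis assigns the timepoint reviews to the Sponsor's "Medical Expert(s) and/or the Data Safety Monitoring Board".

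**The concern.** Section 7.1 presents the ad hoc triggers as one of the key measures protecting patients in this first-in-human study. Until the first scheduled meeting, they are the only stated requirement in the protocol for the independent board to convene. Both escalation decisions, low to medium and medium to high, fall before that meeting and rest with the sponsor.

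Elsewhere the protocol uses both terms. The sponsor's second-cycle review in Section 7.1 covers serious and severe events, and the rules for withholding infusion in Section 14.5 name a severe infusion-related reaction and a serious adverse reaction separately. Only the trigger that calls in the independent board leaves seriousness out, which looks like an oversight.

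The case left over is foreseeable. Section 13.4.6 accepts that "Despite all due care, there is a certain risk of the possible transmission of germ components", and Appendix 24.7 is titled "Handling of sterility testing positive results in/during manufacturing and after IMP administration". A positive culture after infusion in a patient with few symptoms is serious under Section 13.1.2 but could be graded below 3.

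**Working it through.** The plan states no figure to reproduce. The check runs one test case through each rule: a single patient with one IMP-related serious adverse event of Grade 1 or 2.

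| Trigger (synopsis) | Needs | Test case | Met? |
|---|---|---|---|
| Severe, related | 1 patient, severe | Grade 1 or 2 | No |
| Moderate, related | 3 patients, same dose level | 1 patient if Grade 2; 0 if Grade 1 | No |
| MRI | 3 patients, more than 5 new lesions | Not an MRI finding | No |
| Relapse | Confirmed severe relapse | Relapses are not adverse events (Sections 12.1.1.2, 13.1.1) | No |

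No meeting is required.

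**The moderate trigger as a backstop.** Planned first-cycle group sizes are 2, 3 and 4, total 9 (Section 7.1). With a threshold of 3 at one dose level, the low-dose group cannot reach it (2 < 3) unless patients are replaced under Section 9.3.1. All 3 medium-dose patients, or 3 of the 4 high-dose patients, would have to qualify.

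**How much seriousness the severity trigger already captures.** Setting Section 13.1.2 beside Table 13-1, with severe read as Grade 3 or higher:

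- Death corresponds to Grade 5 and life-threatening to Grade 4.
- Hospitalization and disability both correspond to Grade 3 descriptors.
- Medically important events are uncertain. A site that treats the event as medically significant would grade it 3 and the trigger would fire; a site that grades by symptoms might not.
- Suspected transmission of an infectious agent is an event of this last kind, so it shares the uncertainty. Section 13.1.2 calls it serious with no condition on grade.

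The gap is therefore a medically important event, including suspected transmission with mild symptoms, that the site does not grade 3.

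**Where the triggers are written down.** Section 13.4.5 sends the reader to Section 19.1.3 for the rules that prompt a DSMB review. Section 19.1.3 gives the schedule, the possible recommendations and the listings, but not the triggers. Sections 13.4 and 13.6 also point there. The synopsis is the only place in the protocol where the list appears.

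**The case against.** The strongest reply is that such an event would not be missed. Safety is assessed after each patient in every dose group (synopsis) and between patients (Section 7.1). Related serious events enter the sponsor's second-cycle review. A serious reaction stops further infusions in that patient (Section 14.5). Serious events are reported within 24 hours and, if unexpected, go to authorities, ethics committees and investigators (Section 13.2.2). The Steering Committee is "to review safety data; in a blinded manner. This review is typically done blinded to treatment allocation". Sections 13.4 and 13.6 describe DSMB oversight as continuing through the study, and the wording of the synopsis lets the board join timepoint reviews. Finally, the Charter holds the details of the board's scope and timing (SAP Section 6), and neither it, the Appendix 24.7 flowcharts nor Figure 7-1 can be seen here.

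Most of this stands, and it makes the consequence small. It does not remove the point. The routes that can be read lead to the sponsor, the site, the Steering Committee or the authorities; none requires the independent board to meet. The board's part in timepoint reviews is optional, and the sections on continuing oversight refer to Section 19.1.3, which adds no trigger.

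A reader might also infer that Grade 4 and 5 events fall outside the first trigger, because severe is the Grade 3 label in Table 13-1. The documents do not support that. SAP Section 5.5.1 equates severe with Grade 3 or above in defining events of special interest, and a one-patient rule that skipped fatal events would make no sense.

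**Conclusion.** The point holds as a minor one. On the protocol text, none of the four triggers uses seriousness, and one related serious event below Grade 3 does not by itself require a DSMB meeting before the first scheduled review.

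It would be tempting to conclude that serious events go unreviewed, or that the trial has no seriousness trigger at all. Neither follows. Review by other bodies is well specified, and the unseen Charter, Appendix 24.7 flowcharts and Figure 7-1 may supply the missing route; the finding is only that the readable protocol text does not.

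The size is narrow: in practice, medically important events that a site does not grade 3. The documents give no rate for these, and the conclusion does not depend on one. It assumes that severe means Grade 3 or higher, the reading more favourable to the plan.

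**What to change.** Reword the first trigger to: *at least 1 patient with an AE of Grade 3 or higher, or any serious AE, assessed as related to CLS12311/placebo*. This also settles the grade question and matches the two-level related/not related scale in Section 13.1.4. Place the full trigger list in Section 19.1.3, where Section 13.4.5 says it is, and in the DSMB Charter.

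The cost is one line of wording, a copied list, a protocol amendment under Section 19.7 and possibly one extra ad hoc meeting of the existing board.

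The SAP revision history records changes after a data review, dated 29 January and 3 February 2026, so dosing may already be complete. That is an inference, since no last-visit date is given. If dosing is complete, no amendment is needed: confirm instead that any related serious event, and any related Grade 4 or 5 event, was sent to the DSMB. With 9 planned patients that check is small.
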